We hypothesize that administration of TXA will reduce perioperative bleeding in osteotomy procedure with minimal side effects. As a result, swelling and postoperative pain will decrease thus improving postoperative outcomes. While TXA has been used in various orthopedic surgeries to reduce bleeding, no study has investigated the efficacy of TXA during a TTO procedure and TXA during HTOs have limited available studies. The available literature shows perioperative bleeding and hematoma significantly decreased during HTO procedures³. By comparing high tibial osteotomy patients to tibial tubercle osteotomy patients, we will determine if there is a difference in efficacy or if both cohorts will be similarly affected.

Study Design

This is a single-center, prospective cohort study. Patients will be assigned to their cohorts based on diagnosis and appropriate treatment as determined by the surgeon. Patients will be consented in the study once they are scheduled for either a HTO or TTO, therefore this will not be a randomized study. The study is comparing blood loss and postoperative pain after TXA administration in patients receiving a high tibial osteotomy (HTO) to patients receiving a tibial tubercle osteotomy (TTO) with or without medial patello-femoral ligament (MPFL) reconstruction. One gram of intravenous tranexamic acid will be administered before tourniquet inflation and 1 gram of IV TXA before closure of the incision. Patients will be asked on postoperative day 1, 2 and 7 to rate their pain according to the VAS scale. Patients will have their knee swelling measured immediately postoperatively and at their one-week follow up visit. The swelling ratio is defined as the postoperative mean circumference of upper pole of patella and lower pole of patella divided by the preoperative values.

Primary Objective

The primary objective of the study is to determine if there are any differences in blood loss between patients undergoing high tibial osteotomy (HTO) and tibial tubercle osteotomy (TTO) with or without medial patello-femoral ligament (MPFL) reconstruction.

Secondary Objective

Secondary objective of the study is to determine if there is a difference in post operative pain and swelling between patients undergoing HTO compared to patients undergoing TTO.

II. CHARACTERISTICS OF THE RESEARCH POPULATION

Number of Subjects

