Patients indicated and scheduled for a high tibial osteotomy or tibial tubercle osteotomy with or without medial patello-femoral ligament reconstruction will be identified from faculty surgeon case logs at the NYU Langone Health, Langone Orthopedic Hospital Sports Medicine Division. After informed consent is obtained, a chart review of patients' medications and past medical histories will be reviewed based on their electronic medical records to identify any current pain medications or exclusion criteria. Patients will be in the study for 1 week, until their first follow up visit.

Patients will be given 1 gram of intravenous tranexamic acid (TXA) before tourniquet inflation and 1 gram of IV TXA before closure of the incision. Immediate post-operative management will not be affected by this study. The study team will not be blinded to the study as there is no randomization to each cohort. All patients will receive a standardized regimen of aspirin for DVT prophylaxis and Percocet for pain management, which is standard of care post-operative treatment.

Information to be recorded pre-operatively includes age, sex, height, weight, BMI, and American Society of Anesthesiology (ASA) classification. Intra-operative information will also be recorded, including operative time, and estimated blood loss. During the surgery, a suction device is utilized to remove excess blood from the surgical site and sucked into the suction drain and placed into a measuring cup. We will measure the perioperative blood loss by look at the measuring cup and seeing how much blood is inside. Knee swelling postoperatively will be measured using the swelling ratio. The swelling ratio was defined as the circumference of the operative limb divided by the circumference of the contralateral limb. Pain severity scores at rest will be assessed by use of a visual analog scale (VAS; 0 = no pain, 10 = worst pain imaginable) at 0.5, 1, 1.5, 2, 4, 6, 24, and 48 hours as well as 7 days after surgery. Percocet consumption will be recorded at 24 hours, 1 day, 2 days and 7 days after surgery. Incidence of TXA-related side effects (nausea/vomiting, itching, anxiety, increased thirst, rapid heartbeat) in the first 24 hours will be noted. Time to discharge from the post-anesthesia care unit (PACU) and time to discharge from the hospital will be recorded.

Analysis and Data Monitoring

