Data monitoring will be done by [name], the principal investigator. He will review the following accumulated data quarterly.

He will monitor whether or not:

1. Collection and storage of patient data was performed in a sensitive and secure manner, as defined in the informed consent form and protocol, ensuring information is stored on REDCap.
2. All study activities were conducted with primary emphasis on patient care and wellbeing, ensuring the patients are not in discomfort and have an abnormally high VAS following the surgery.
3. If there were any adverse events, and if so were addressed appropriately and per protocol
4. The risk/benefit to patients has remained the same throughout the course of the study.

The study will be stopped if there are unexpected severe AE's in more than one patient. Adverse events will be defined as negative reactions to the intravenous TXA during or after surgery, including seizures, vision problems. We will submit summaries of data and safety monitoring annually.

Data Analysis

According to a post hoc power analysis calculating the effect size using our preliminary data, >15 patients are required with $d=0.6$ to obtain a power of 0.80 and an alpha value of 0.05. Therefore we are including an additional 5 patients per group to account for patients that may be

lost to follow up. Statistical analysis will be performed using chi-squared and/or fisher's exact testing depending on size for binary variables. Continuous variables will be compared with paired t-tests if the data is approximately normally distributed. If the data is not normally distributed, Mann-Whitney tests will be used. All protected health information will be removed prior to statistical analysis. We will use patient subjective pain, perioperative blood loss and knee swelling data as statistical endpoints. Subjective pain will be measured with the VAS (visual analogue scale), perioperative blood loss will be measured looking at blood loss from the suction drain after surgery. The swelling ratio is defined as the postoperative mean circumference of upper pole of patella and lower pole of patella divided by the preoperative values according to our previous study. The endpoints must be statistically significant between the two cohorts to show TXA is effective.

Data Storage and Confidentiality

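### The primary blood-loss value is an uncorrected, unblinded visual reading of the suction cup, and its error could differ between HTO and TTO

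*Combined protocol and SAP*

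**What the plan says.** The Primary Objective (section I) is a comparison of blood loss between the HTO and TTO cohorts. The TTO cohort may include patients with an added ligament (MPFL) reconstruction.

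The measurement is described in two places:

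- Section III, Methods and Procedures, places collection during the operation: "a suction device is utilized to remove excess blood from the surgical site and sucked into the suction drain and placed into a measuring cup". The reading rule follows: "We will measure the perioperative blood loss by look at the measuring cup and seeing how much blood is inside".
- Section III, Data Analysis, names the same source but words the timing differently: "perioperative blood loss will be measured looking at blood loss from the suction drain after surgery".

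Three other statements bear on the point:

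- Methods and Procedures lists a further blood-loss item: "Intra-operative information will also be recorded, including operative time, and estimated blood loss". It gives no separate method for this item and does not say whether it is the cup reading.
- The same section states: "The study team will not be blinded to the study as there is no randomization to each cohort".
- Study Design (section I) states: "Patients will be assigned to their cohorts based on diagnosis and appropriate treatment as determined by the surgeon".

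The documents nowhere mention irrigation fluid, sponges, weighing, change in haemoglobin or a blood-volume formula.

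**The concern.** A suction cup holds whatever was suctioned and misses whatever was not. If fluid other than blood enters it, the rule does not say whether the reader records the total volume or judges how much of it is blood. Blood left on sponges or drapes, or in the joint, is not counted.

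In a randomised comparison of one operation, much of this error would be expected to fall equally on both arms. Here, cohort and operation are the same thing. If fluid use, uncollected blood or the reader's judgement varies with the operation, the resulting error is completely confounded with the primary contrast, and a larger sample would not remove it. The reader also knows which operation was done.

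Data Analysis goes on to treat significant differences between the cohorts as the evidence that TXA works. A measurement artefact that reached significance could therefore be reported as a drug effect. Unless the component volumes are recorded at surgery, the artefact could not be checked afterwards.

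**Working it through.** **The plan's own figure.** The documents give no figure for blood loss, irrigation or sponge loss, so there is none to reproduce on this point. The only computed figure is the sample size: more than 15 patients at d = 0.6, power 0.80 and alpha 0.05. A two-sided two-sample t-test needs 45 per group at d = 0.6, so the figure is not reproduced for two independent cohorts. That is a separate matter, and nothing below depends on it. The planned 20 per cohort is used only as the sample size.

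**Error in the contrast, in mL.** Let ΔV be the between-cohort difference in mean irrigant in the cup, m the fraction of it read as blood, and ΔS the between-cohort difference in mean blood not suctioned.

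- Error under the current rule = m·ΔV − ΔS.
- Assume 500 mL in one operation and 1,000 mL in the other, so ΔV = 500 mL, and set ΔS = 0.
- If the reader judges the blood content and counts 10% to 30% of irrigant as blood: 0.10 × 500 = 50 mL to 0.30 × 500 = 150 mL.
- If the total volume is recorded as blood (m = 1): 500 mL.
- If ΔS were 50 to 150 mL in the same direction, it would cancel the 50 to 150 mL error. A larger ΔS would reverse its sign.

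All these volumes and fractions are assumptions, so neither size nor direction can be fixed from the documents.

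**Error after subtracting irrigation used.** Let ΔI be the difference in irrigation used and r the fraction that reaches the canister. Canister volume minus irrigation used has contrast error −(1 − r)·ΔI − ΔS. Take 500 and 1,000 mL as the volumes used and ΔS = 0:

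| r | Error in the two cohorts (mL) | Absolute false difference after subtraction (mL) | Absolute false difference if total volume is read uncorrected, r·ΔI (mL) |
|---|---|---|---|
| 1.0 | 0 and 0 | 0 | 500 |
| 0.9 | −50 and −100 | 50 | 450 |
| 0.7 | −150 and −300 | 150 | 350 |

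On these inputs, subtraction is clearly better than an uncorrected total. It is not necessarily better than a reader who misjudges only 10% to 30% of the irrigant, since both leave 50 to 150 mL. What it adds is that the residual can be examined. With canister volume T and recorded irrigation I, T − f·I = (T − I) + (1 − f)·I, so the contrast can be recomputed for any assumed recovery f.

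**Scale-free check.** Let b be the differential error in SD units, with no true difference, 20 per group, a two-sided two-sample t-test and alpha 0.05. The noncentrality is b·√(20/2), on 2 × 20 − 2 = 38 degrees of freedom.

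| b (SD, assumed) | Chance of p<0.05 |
|---|---|
| 0 | 5% |
| 0.10 | 6.1% |
| 0.25 | 12.0% |
| 0.50 | 33.8% |
| 1.00 | 86.9% |

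**Error that is equal in both cohorts.** This only costs power. With reliability R, the standardised effect becomes d·√R. At true d = 0.6 and 20 per group, power is 45.6% at R = 1. At R = 0.8 the effect is 0.6 × √0.8 = 0.537 and power is 38.0%.

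**The case against.** The strongest objection is that the premise is not in the documents. They never say that irrigation or sponges are used, or in what amounts, so a difference by operation is possible but not shown. This stands. It rules out a claim that the primary contrast is biased, though not the need for a stated rule.

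Second, the rule asks the reader to see how much blood is in the cup, so its target is blood and not total fluid. A reader might infer that the cup value is not blood loss at all. The text does not support that: the value is an unvalidated proxy that can over-count or under-count.

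Third, the relevance of irrigation depends on the collection window. If Data Analysis means drain output after the operation, intraoperative irrigant and sponge loss are largely beside the point. This also stands, and is why the two sections must be reconciled together.

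Fourth, a reader might infer that two rival primary values exist. The estimated blood loss is followed directly by the description of the cup, so the natural reading is one item and its method, and Data Analysis names only the drain. A clarifying sentence is enough.

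Finally, subtracting irrigation is not exact: unrecovered fluid leaves an error that can itself differ by cohort, as the first table shows. The residual has to be disclosed and varied in a sensitivity analysis.

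**Conclusion.** The concern holds as a weakness in the definition of the primary measurement. Both sections take the value from the suction cup or drain alone. Methods and Procedures has it read by eye by an unblinded team, with no correction for non-blood fluid and no count of blood that was not suctioned. An error that varied by operation would be confounded with the HTO versus TTO contrast.

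Its size and direction are unknown. The mL figures rest on assumed volumes, an assumed reading fraction and an assumed recovery. The false-positive rates of 12.0% and 33.8% rest on assumed differential errors of 0.25 and 0.5 SD and a two-sided two-sample t-test. A reader might infer that the error certainly fails to cancel, or that the contrast is off by 50 to 150 mL; the documents support neither. The change should be made because it is cheap and because the missing volumes cannot be reliably reconstructed after surgery.

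**What to change.** Change Methods and Procedures and Data Analysis together, so that both carry one definition:

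1. **Primary value.** Primary blood loss is the measured total canister volume minus the recorded irrigation volume, read at one stated time point by the same rule in both cohorts.
2. **Collection window.** State whether collection is intraoperative, postoperative or both, and reconcile the two sections. If any of it is postoperative, say how irrigation enters the calculation for that part.
3. **Irrigation field.** Record irrigation volume as its own field. Add a sensitivity analysis that repeats the primary contrast with T − f·I for f from, for example, 0.70 to 1.00.
4. **Sponges.** Record the sponge count in both cohorts as a descriptive check. Add sponge loss to the primary value only if an explicit conversion rule is written down.
5. **Estimated blood loss.** State whether this is the same value or a separate one, and if separate, that it is supportive only.

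The cost is one or two extra fields on the operative form. Some error from unrecovered irrigant will remain, and subtraction adds some measurement noise. No treatment changes. The change is worth making before further cases are measured.

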Reducing Hemarthrosis in High Tibial Osteotomy and Tibial Tubercl Osteotomy by the Administration of Intravenous Tranexamic Acid: A Prospective, cohort study

Regulatory Sponsor: *NYU Langone Health
Langone Orthopedic Hospital
[name]
New York, NY 10003*

Principal Investigator: *[name]
Division of Sports Medicine
New York University Hospital for Joint Diseases
New York, NY 10003
Office: [contact]*

Protocol Number: **18-00535**

Version Date: **June 4, 2018**

NCT03606109

I. PURPOSE OF THE STUDY AND BACKGROUND

Purpose

The purpose of the proposed study is to evaluate the effects of administering intravenous tranexamic acid (TXA) to patients undergoing high tibial osteotomy (HTO) and tibial tubercle osteotomy (TTO) to minimize hemarthrosis within the knee joint and post operative pain and swelling.

Rationale

High tibial osteotomy is a procedure performed to correct varus malalignment and slow the progression of medial osteoarthritis or correct knee instability caused by varus malalignment¹. Tibial tubercle osteotomy is a procedure performed to treat patellar instability or overload of the patella². The tibial tubercle is a bony prominence where the patella attaches found on the anterior tibia, inferior to the knee joint. Both patients requiring HTO and TTOs suffer from chronic knee pain. During the process of an osteotomy, extensive bone bleeding can occur due to the opening gap³. As a result, complications of both procedures include postoperative bleeding and swelling of the knee joint, which prolongs healing and the rehabilitation process.

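### As described, the primary blood-loss variable is mainly intraoperative and its window is not fixed, so it cannot support a conclusion about hemarthrosis

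*Combined protocol and SAP*

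**What the plan says.** The title begins "Reducing Hemarthrosis in High Tibial Osteotomy". The Purpose paragraph of Section I says the drug is given "to minimize hemarthrosis within the knee joint and post operative pain and swelling". The Rationale that follows says that "complications of both procedures include postoperative bleeding and swelling of the knee joint". The target is therefore bleeding in the joint, with an emphasis on what happens after the operation.

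The Primary Objective asks whether blood loss differs between HTO and TTO patients. It gives no time window and no method of measurement.

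Section III, Methods and Procedures, supplies a method. It first states: "Intra-operative information will also be recorded, including operative time, and estimated blood loss". It then describes a suction device used during surgery, which takes blood from the surgical site to the suction drain and into a measuring cup, and concludes: "We will measure the perioperative blood loss by look at the measuring cup and seeing how much blood is inside".

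The Data Analysis paragraph of the same section names blood loss as one of three statistical endpoints, with pain and swelling, and says "perioperative blood loss will be measured looking at blood loss from the suction drain after surgery".

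**The concern.** The variable chosen to answer the primary question does not appear to cover the bleeding named in the title and purpose. A cup filled by suction during surgery stops filling when the wound is closed. Bleeding into the joint after that point goes unrecorded by it.

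The plan also does not settle what the variable is. It is listed as an intraoperative item, called perioperative, and then tied to a drain after surgery. If the report speaks of hemarthrosis or perioperative bleeding on the strength of an intraoperative cup reading, its main conclusion will claim more than was measured. If the after-surgery wording were taken to mean a second source, two quantities could be recorded under one name. That second risk depends on how staff read the text.

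**Working it through.** No arithmetic decides this point, so the relevant sections are set side by side.

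1. **Target.** Title and Purpose: hemarthrosis. Rationale: postoperative bleeding and swelling. Primary Objective: blood loss, window unstated.

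2. **Collection.** Methods and Procedures: suction from the surgical site during the operation, into a cup, read by eye. This is the only blood-collection procedure in the document.

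3. **The Data Analysis wording.** It allows two readings.
   - (a) The words about timing say when the container is read. Methods already uses the term suction drain for the intraoperative device, so this is the same cup looked at once the operation is over.
   - (b) The words about timing say when the blood was lost. This would need a postoperative drain. The document describes no drain placement, collection period or removal.

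   Reading (a) is the natural one. Reading (b) is not excluded.

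4. **Estimated blood loss.** It is listed among intraoperative items directly before the description of the suction device. The likeliest reading is one variable followed by its method, but the text does not say so, and the next label used is perioperative.

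5. **What each reading captures.**
   - Under (a): blood suctioned up to closure. Blood collecting in the joint afterwards is not included.
   - Under (b): some bleeding after closure, over a period that is not defined.

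6. **Other measures after closure.** Section III also records pain scores, Percocet consumption, side effects in the first 24 hours, discharge times and knee swelling. It describes no joint aspiration, imaging, hemoglobin change or calculated blood loss. That leaves the swelling ratio, measured immediately after surgery and at one week, as the one item bearing on blood in the joint. It belongs to the secondary objective.

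7. **The swelling ratio has two definitions.** Study Design and Data Analysis divide the postoperative mean circumference (upper and lower pole of the patella) by the preoperative value: R1 = C_post / C_pre. Methods divides the operative limb by the contralateral limb: R2 = C_post / C_contra, with no measuring level stated. Taking the same postoperative circumference, R2 / R1 = C_pre / C_contra. The two agree only if the knee to be operated on had the same circumference before surgery as the other knee, which the plan does not establish.

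8. **Size.** The documents give no blood volumes, so the amount missed after closure cannot be calculated. The sample-size statement (d = 0.6) does not name the endpoint behind the effect size, so it does not show which blood-loss measure was intended.

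**The case against.** The best defense is that the primary objective promises blood loss, the hypothesis speaks of perioperative bleeding, and neither makes hemarthrosis the primary variable. The Purpose also names pain and swelling, and both are collected and analyzed. Since Methods and Data Analysis share the term suction drain, the plan can be read as describing one container throughout.

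Much of this stands. A reader might infer that the plan gives three conflicting definitions, or that staff will mix cup and drain volumes. The text shows an ambiguity, and the mixing is only a possibility. A reader might also infer that the cup volume says nothing about hemarthrosis. What the documents support is that it does not measure it.

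The defense does not remove the mismatch, however. The more firmly one holds that there is a single intraoperative container, the clearer it is that bleeding after closure is left out.

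A stronger reading is that the measure cannot register any effect of the second dose, described as "1 gram of IV TXA before closure of the incision". The documents do not support it. Bleeding between that dose and closure can still be suctioned. Neither the interval from dose to closure nor the time of tourniquet release is given. The 3-hour mean duration of effect is stated to justify the recovery-unit stay and cannot be turned into a share of the effect missed. Moreover, both cohorts receive both doses and there is no untreated group, so no endpoint in this design could isolate the effect of one dose. That limit belongs to the design.

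**Conclusion.** The concern holds in this form: the primary blood-loss variable, as described, is mainly intraoperative, its source and reading time are not stated consistently, and on the natural reading it does not measure joint bleeding after closure. It can serve a comparison of HTO and TTO blood loss within a defined window. It cannot support a conclusion about the hemarthrosis in the title and purpose.

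The effect is on what may be concluded and cannot be expressed as a volume. It applies to the primary variable in both cohorts, 20 + 20 = 40 planned patients. The conclusion assumes that suction drain means the intraoperative device in both places. If the sponsor intended a postoperative drain, the mismatch with hemarthrosis is smaller, but the variable is then undefined for want of a collection procedure and period. The text should be corrected in either case.

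**What to change.** - Give one source and one reading time for blood loss, in the same words, in the Primary Objective, Methods and Procedures, and Data Analysis.
- If the suction canister is meant, call the variable intraoperative blood loss and read it at wound closure, net of irrigation fluid if any is used (the documents do not say). State that estimated blood loss is the same variable, or drop it.
- If a postoperative drain is meant, say so in Methods and give its collection period.
- Limit the primary conclusion to the HTO-versus-TTO difference in blood loss in that window, and bring the closing sentence of Data Analysis, which treats significance between cohorts as showing that the drug works, into line with that limit.
- Choose one definition of the swelling ratio, with its reference value and measuring level, and use it in Study Design, Methods and Data Analysis. Then identify the ratio as the only measure in the study bearing on hemarthrosis, and an indirect one.

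The cost is a few sentences of wording and a narrower headline claim. No added test, imaging or visit is needed.

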The total number of subjects enrolled will be approximately forty (40) patients, with 20 patients in the HTO cohort and 20 patients in the TTO cohort, calculated by post hoc analysis. The Patients will be recruited from routine clinical practice at The NYU Langone Health, Langone Orthopedic Hospital, Sports Medicine Division.

Gender of Subjects

Men and women will be included in this study.

Age of Subjects

Subjects included study will be at least 18 years of age.

Racial and Ethnic Origin

There are no enrollment restrictions based on race or ethnic origin.

Inclusion Criteria

Patients will be screened for eligibility using the following criteria. All study subjects must meet the following inclusion criteria:

- Patients undergoing a high tibial osteotomy (HTO)
- Patients undergoing tibial tubercle osteotomy (TTO) with or without medial patello-femoral ligament (MPFL) reconstruction
- Patients ages 18-60, inclusive

Exclusion Criteria

Patients meeting the following criteria will be excluded from participation in this study:

- Legally incompetent or mentally impaired (e.g., minors, Alzheimer's subjects, dementia, etc.)
- Younger than 18 years of age
- Older than 60 years of age
- Any patient considered a vulnerable subject including: pregnant women or fetuses, children, cognitively impaired adults, prisoners
- history of coagulation abnormalities and thromboembolic disease or current abnormal coagulation test values
- history of stroke or acute coronary syndromes within 3 months before surgery
- Preoperative (chronic) anticoagulation therapy
- Abnormal coagulation profile
- Renal failure (serum creatinine $> 250 \mu\text{mol/L}$ [2.83 mg/dL]) or liver cirrhosis
- Sickle cell disease
- Patients with a history of hypersensitivity to Percocet and/or TXA

Vulnerable Subjects

We do not intend to enroll vulnerable subjects.

Subject withdrawal criteria. Patients are free to withdraw at any time from the study.

III. METHODS AND PROCEDURES

Methods and Procedures

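### The swelling ratio, a named endpoint, has two incompatible definitions, and the preoperative circumference that one of them needs is neither listed nor scheduled

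*Combined protocol and SAP*

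**What the plan says.** The ratio is defined in three places.

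- **Study Design (section I):** the "postoperative mean circumference of upper pole of patella and lower pole of patella divided by the preoperative values".
- **Methods and Procedures (section III):** "Knee swelling postoperatively will be measured using the swelling ratio", followed directly by "The swelling ratio was defined as the circumference of the operative limb divided by the circumference of the contralateral limb". No measurement level and no averaging are given.
- **Data Analysis (section III):** the "postoperative mean circumference of upper pole of patella and lower pole of patella divided by the preoperative values according to our previous study".

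On timing, Study Design says: "Patients will have their knee swelling measured immediately postoperatively and at their one-week follow up visit". On baseline data, Methods and Procedures says: "Information to be recorded pre-operatively includes age, sex, height, weight, BMI, and American Society of Anesthesiology (ASA) classification". Neither sentence mentions a preoperative knee circumference.

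On the role of swelling, the Secondary Objective is to "determine if there is a difference in post operative pain and swelling between patients undergoing HTO" and those undergoing TTO. Data Analysis names swelling as a statistical endpoint alongside pain and blood loss, and makes the claim that TXA works depend on significant differences between the cohorts.

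**The concern.** The two definitions have different denominators: the same knee before surgery, or the other limb. They also differ in how the numerator is specified. One averages two named patellar levels, and the other names no level. They are different endpoints under one name, and no text says that one replaces the other or that both will be analysed.

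The contralateral ratio mixes postoperative swelling with any difference between the limbs that existed before surgery. The cohorts are formed by diagnosis and are not randomised, so nothing in the design balances that difference between HTO and TTO. The study team is also unblinded. With two definitions on file, the choice between them could be made after the data are seen.

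There is a practical risk too. The section that tells staff how to measure swelling calls for no baseline. If the analysis is meant to use the post/pre ratio and the baseline was not taken, the endpoint cannot be computed for that patient. A contralateral reading can still be made at a postoperative visit. A missed preoperative reading is lost.

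**Working it through.** The documents give no circumference, limb asymmetry or standard deviation for the ratio, so there is no plan figure to reproduce. The check compares the definitions algebraically and then illustrates the result with assumed values.

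**Notation**, all at the same measurement level:

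- post = operative-knee circumference after surgery
- pre = operative-knee circumference before surgery
- contra = contralateral circumference when post is measured
- A = post/pre (Study Design, Data Analysis)
- B = post/contra (Methods and Procedures)
- k = pre/contra

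**Identity.** B/A = (post/contra) / (post/pre) = pre/contra = k, so B = A × k. This needs no assumption about the size or form of the swelling. A and B agree only when k = 1. A 1% limb difference before surgery changes B by 1% relative to A.

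**Illustration 1: fixed swelling.** A = 1.05 and the values of k are assumed.

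| Preoperative asymmetry | k | B = 1.05 × k |
|---|---|---|
| −5% | 0.950 | 0.9975 |
| −4.8% | 1/1.05 = 0.9524 | 1.0000 |
| −2.5% | 0.975 | 1.0238 |
| 0% | 1.000 | 1.0500 |
| +2.5% | 1.025 | 1.0763 |
| +5% | 1.050 | 1.1025 |

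**Illustration 2: fixed contralateral ratio.** With post = 42 cm and contra = 40 cm (assumed), B = 42/40 = 1.050 in every row.

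| pre (cm) | A = 42/pre |
|---|---|
| 39 | 1.077 |
| 40 | 1.050 |
| 41 | 1.024 |
| 42 | 1.000 |

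The same B can go with clear swelling or with none, as measured by A.

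**Effect on the cohort comparison.** On the log scale, log B = log A + log k. The HTO–TTO difference in mean log B is therefore the difference in mean log A plus the difference in mean log k, and the two definitions give the same contrast exactly when mean log k is equal in the cohorts. On the raw scale, E[B] = E[A]E[k] + cov(A, k). There, a cohort difference in the covariance also matters, and a common mean k other than 1 rescales a true difference. None of these quantities is in the documents, so no cohort-level shift can be given.

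**Baseline readings.** Number of Subjects gives the total: "The total number of subjects enrolled will be approximately forty (40) patients". The post/pre version needs 40 patients × 2 patellar poles = 80 preoperative readings. The contralateral version needs 0.

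**The case against.** The strongest reply is that the text largely settles the matter. Two of the three statements agree, and one of them is in Data Analysis, which governs what is tested. The Methods sentence is in the past tense among future-tense procedures, which would fit carried-over wording. On this reading, one sentence needs correcting. That is a fair account of the likely intent, and it supports post/pre as the default. It does not remove the problem, because the odd one out is the instruction on how swelling is measured.

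On the baseline, the preoperative list is introduced as what is included, so it may not be exhaustive. The post/pre definition itself implies a baseline, and in Study Design it closely follows the measurement schedule. The case report form is not among the documents. All this stands: the documents do not show that the baseline is omitted, only that it is not explicitly listed or scheduled.

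The illustrations rest on assumed values, and nothing in the documents supports an asymmetry of any particular size or direction. This also stands. They show that the two ratios are not equivalent, not how much harm results. The count of 80 readings measures the work needed for the fix, not the size of an error.

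The previous study mentioned in Data Analysis is not described, but the formula is written out, so little hangs on that. The plan also does not say which of the two swelling times is the endpoint. That is a separate matter, and settling the formula will not resolve it.

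**Conclusion.** The concern holds, with high confidence in the contradiction itself. Staff who follow Methods and Procedures will produce a different quantity from the one Data Analysis says will be tested. The ratio between the two is exactly pre/contra at the same level and time. The size and direction of any effect on the HTO–TTO comparison are unknown, and the documents do not show which ratio is the more variable.

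This should be corrected, but it is not critical to the main result: swelling is a secondary outcome. Loss of the baseline is a risk rather than a demonstrated omission, but one that cannot be repaired after surgery.

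**What to change.** Use one definition throughout. The default, for the sponsor to confirm, is the one already in Study Design and Data Analysis: the mean of the upper-pole and lower-pole circumferences of the operative knee after surgery, divided by the same mean before surgery. Replace the contralateral sentence in Methods and Procedures with it.

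Add operative-knee circumference at both patellar poles to the preoperative data list and to the swelling schedule, taken at the same stated point shortly before surgery in every patient (for example, on the day of surgery before the procedure).

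If the sponsor confirms the contralateral version instead, change Study Design and Data Analysis to match and state the measurement level.

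The cost is a wording change to the protocol and case report form. Under the default it also takes one brief tape measurement at two levels per patient, 80 readings for 40 patients.
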